Moreover, a clear and significant dose-effect curve between adherence rate to ERAS program items and early outcomes was demonstrated (18-20), and recent evidence deriving from retrospective studies suggests that ERAS programs may also offer a definite advantage over long-term survival after colorectal resection for malignancy (21-23). While many studies to date have focused on early outcomes (i.e. earlier return of bowel function, lower complication rates, and/or shorter length of inpatient stay), for the majority of oncologic operations, however, postoperative recovery carries the additional demand of returning the patient to adjuvant oncologic therapies. It is still unclear if ERAS program could improve the failure to “return to intended oncologic therapy” (RIOT) after cancer surgery due to complications and lingering poor performance status (24), that is strongly associated with worse oncologic outcomes, including shortened overall survival (25, 26). Measuring patient-reported outcomes (PROs) addresses the gap in enhanced recovery assessment by incorporation of patient-centered quality into our global assessment of outcomes (27). Taken together, these data establish a paradigm for association of perioperative medical care to long-term oncologic outcomes—revealing how the perioperative care team’s actions over a relatively short number of days and hours around the time of a cancer surgery can improve cancer-specific survival. The concept is that various perioperative techniques, protocols, and agents will blunt the patient’s perioperative stress response, reduce complications, and improve functional recovery after surgery. Together, these effects allow more people to RIOT in a more timely fashion and in a more complete way. To the extent that the combination of preservation of immune competence and more reliable return to adjuvant therapies then reduce recurrence rates, longer and more meaningful survivals may be achieved.

Therefore, we planned this study to prospectively evaluate the impact of adherence to ERAS program items after colorectal resections on PRO in the whole population and on failure to RIOT for malignant disease.

METHODS

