Prospective enrollment from November 2020 to October 2021 in 60 Italian surgical centers. All patients undergoing elective or delayed urgency colorectal surgery with anastomosis will be included in a prospective database after written informed consent. A total of 3,000 patients is expected based on a mean of 50 cases per center.

Inclusion criteria

1. Patients submitted to laparoscopic/robotic/open/converted ileo-colo-rectal resection with anastomosis, including planned Hartmann's reversals.
2. American Society of Anesthesiologists' (ASA) class I, II or III
3. Elective or delayed urgency surgery
4. Patients' written acceptance to be included in the study.

Exclusion criteria

1. American Society of Anesthesiologists' (ASA) class IV-V
2. Emergent surgery
3. Pregnancy
4. Hyperthermic intraperitoneal chemotherapy for carcinomatosis.

Outcome measures

1. Preoperative risk factors for morbidity (age, gender, obesity, nutritional status, diabetes, cardiovascular disease, chronic liver disease, renal failure, inflammatory

bowel disease, perioperative steroid therapy, ASA class I-II vs III, SARS-CoV-2 infection)

2. Operative parameters (approach, procedure, anastomotic technique, length of operation, pTNM stage)
3. Adherence to ERAS program (28, 29) items (Tab.1).

Endpoints

Primary

1. Patient-related outcomes measures (PROMs):
 - a. Euro-QoL Group EQ-5D-5L (EQ-5D-5L, 32);
 - b. MD Anderson Symptom Inventory for gastrointestinal surgery patients (MDASI-GI, 33);
 - c. Functional Assessment of Cancer Therapy – Colorectal (FACT-C, 34)
2. Return to intended oncologic therapy (RIOT, 24)

Secondary

3. Anastomotic leakage rate
4. Minor and major complication rates according to Clavien-Dindo (35, 36) and JCOG (37) classification
5. Overall length of postoperative hospital stay (including any readmission)
6. Difference between date of readiness for discharge (RFD, 38) and date of actual discharge
7. Readmission and reoperation rates
8. Comparison of two nutritional status scores, MNA-SF (30) and PNI (31), regarding anastomotic leakage, minor and major complication rates and RIOT (24)

9. Impact of anastomotic testing through air-leak test (ALT) and near-infrared fluorescence (NIR) narrow-band imaging (NBI) using indocyanine green (ICG) on anastomotic leakage rates

Recorded data and follow-up

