Potential patient-specific and intraoperative risk factors will be recorded: gender, body mass index, nutritional status, frailty (39), surgical indication (cancer, polyps, chronic inflammatory bowel disease, diverticular disease), use of steroids, renal failure and dialysis, cardiovascular or respiratory disease, American Society of Anesthesiologist class, bowel preparation, type of approach, level of anastomosis and technique (mechanical or hand-sewn, intra- or extra-corporeal), operative time, presence of drainage, and perioperative blood transfusion(s). During the postoperative period, patients will be examined by the attending surgeon daily. Fever (central temperature > 38 °C), pulse, abdominal signs, bowel movements, volume and aspect of drainage (if present) will be recorded daily. The local attending surgeon will make any decision for complementary exams and imaging according to his own criteria, the only exception being the creation of a proximal diverting stoma at operation, that mandates routine check of anastomotic integrity through an intraluminal contrast exam (standard x-rays or CT scan), MRI, or direct endoscopic evaluation three to six weeks after the operation. The rate of any adverse event will be calculated and graded according to Clavien-Dindo criteria (35, 36) and to Japan Clinical Oncology Group Postoperative Complications (JCOG-PC) extended criteria (37), including all anastomotic leaks, wound infection (according to the definitions of the Centers for Disease Control and Prevention and wound culture, 40), pneumonia (clinical symptoms, and physical and radiological examinations), central line infection (positive blood culture), urinary tract infection (positive urine

culture with bacterial count). Patients will be followed-up in the outpatient clinic up to 8 weeks after discharge from the hospital.

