center ethics committee (Comitato Etico Regionale delle Marche - C.E.R.M.) for approval and then registered at ClinicalTrials.gov (NCT04397627). Thereafter, all the participating centers will obtain authorization to participate from the local institutional review board. The results of the study are intended to be presented at national and international medical congresses on corresponding fields of interest (colorectal surgery, abdominal surgery). Written publications of the results are planned within surgical journals. The authorship for written publications is confirmed to all participating investigators, only being granted in the case of substantive contributions to the design, conduct, data analysis, collection and interpretation. Anonymized participant-level datasets will be available after study completion upon reasonable request by contacting the principal investigator.

Statistical Analysis

Quantitative values will be expressed as mean \pm standard deviation (SD), median and range; categorical data with percentage frequencies. For categorical data, analysis will include the use of cross tabulation, chi squared or Fisher's exact test where indicated. Continuous or discrete variables will be analyzed using Student's two-sided t test (allowing for heterogeneity of variances) or with a non-parametric test (Mann-Whitney U test or Kruskal-Wallis test as indicated). Joint and conditional multivariate association between all variables shown to be significant on univariate analysis will be assessed using binary logistic or multiple linear regression. The odds ratio (OR) will be presented followed by 95% confidence interval (95% CI). Concerning comparison of nutritional status scores, areas under the receiver-operating characteristics curve (AUC-ROC) will be calculated for all endpoints, considering values from 0.7 to 0.8 as acceptable, 0.8 to 0.9 excellent, and above 0.9 as outstanding (43). Differences in AUC-ROC curves will be analyzed with the chi-squared test. Optimal cut-off points will be obtained applying Youden's Index (Sensitivity+Specificity-1), choosing those values of the AUC-ROC curve where this index is

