maximal. Negative predictive values (NPV) and positive predictive values (PPV) will also be calculated; finally, a logistic regression model will be built using the presence/absence of endpoint as dependent variable, and nutritional scores \leq or $>$ the cut-off values as explanatory factors; using logistic transformation of the linear predictors, the probabilities of the endpoint related to the different combinations of factors level will be obtained (44). For all statistical tests the significant level is fixed at $p < .05$. Statistical analyses will be carried out using STATA software (Stata Corp. College Station, Texas, USA).

Sample size

Adherence to at least 70% of the ERAS program items was identified as a cut-off for significant improvement of outcomes (18), with a 2:1 expected ratio below:above the cut-off. Estimating a reduction of postoperative PRO from preoperative baseline (1.0) at 0.7 for adherence above the cut-off and at 0.64 for adherence below the cut-off (44), alpha 0.04, beta 0.8, the required sample size is $n=2,406$ (802 cases above 70% adherence and 1,604 below 70% adherence). Reported rates for failure to RIOT and ERAS program items adherence below or above 70% are 13 and 6.5%, respectively (27); the required sample size for evaluation of failure to RIOT is $n=885$ (295 cases above 70% adherence and 590 below 70% adherence). Based on previous iCral observational study on colorectal surgery in Italy (44, 46, 47), the expected ratio of malignant:benign indications to surgery is 70:30 (2,100 resections for malignancy and 900 resections for benign disease on the basis of 3,000 expected cases).

References

2. Kehlet H (2008) Fast-track colorectal surgery. *Lancet* 371:791–793.

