	Antithrombotic prophylaxis	Patient receives graduate compression stockings and/or pneumatic compression device, together with prophylaxis with low molecular weight heparin during the perioperative period, to be extended up to 28 days after surgery in case of malignancy
	Antibiotic prophylaxis	Patient is administered i.v. antibiotic 30 to 60 minutes before incision, according to local protocols
	No bowel preparation	No routine bowel preparation is used, except in case of anticipated need for covering stoma
	Oral carbohydrates load	Carbohydrates rich beverage (12.5% maltodextrins, PreOp™, Nutricia Italy) is given preoperatively (800 ml on the evening before surgery and 400 ml 2 to 3 hours before surgery)
	Preoperative fasting	Preoperative fasting is limited to two hours for clear liquids (water, coffee, tea) and to 6 hours for milk and solid food
Intraoperative	No premedication	No long- or medium-action sedatives. Short and ultra-short acting sedatives (e.g. Lorazepam, Midazolam, Methohexital, Dexmedetomidine, Ketamine) are allowed before performing spinal, epidural or loco-regional anesthesia
	PONV prophylaxis	Postoperative nausea/vomiting prophylaxis is administered according to individual risk assessment (Apfel score) through a multimodal approach
	Normothermia	Body temperature is monitored during surgery, utilizing fluid warmers and/or thermic blankets as necessary
	Standard anesthetic protocol	General anesthesia through short-acting anesthetics, cerebral activity monitoring to enhance recovery and to reduce postoperative delirium, anesthesia level monitoring and complete reversal of neuromuscular blockade
	Intraoperative fluid management	Restrictive fluid therapy (defined as maintenance fluids at <2 ml/kg/h) or goal-oriented fluid therapy (stroke volume)
	Multimodal analgesia	Use of more than two drugs or analgesia strategies (TAP-block or spinal anesthesia for minimally invasive surgery; thoracic epidural anesthesia for open surgery) in order to reduce the use of opiates
	Minimally invasive surgery	Patient submitted to laparoscopic, robotic or video-assisted surgery (conversions to open surgery included on a intention-to-treat basis)
Postoperative	No major opiates	Patient receives no major opiates in the postoperative period
	No nasogastric tube	Nasogastric tube, if used, is removed at the end of surgery
	No drain	No drain is placed in the abdominal cavity (pelvic drain allowed for pelvic surgery with low colorectal anastomosis)

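### Choosing covariates by univariate significance can drop confounders of the ERAS adherence effect and can let parts of the adherence score enter beside it

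*Protocol*

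**What the plan says.** The Background section closes with the aim: to "prospectively evaluate the impact of adherence to ERAS program items after colorectal resections on PRO" and on failure to RIOT in malignant disease. Adherence is therefore the exposure. The Sample size section splits it at 70% of the items in Tab. 1.

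The Statistical Analysis section gives one rule for all multivariable work: logistic or linear regression is to examine the association "between all variables shown to be significant on univariate analysis". It sets no separate screening level; "For all statistical tests the significant level is fixed at" p < .05. It names no variable that must stay in the model and none that must stay out.

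The section Recorded data and follow-up lists the potential risk factors. They include "bowel preparation, type of approach, level of anastomosis and technique", the presence of a drain, operative time and transfusion, alongside frailty, nutritional status, ASA class and indication. The Outcome measures list adds age and pTNM stage and names approach again.

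Tab. 1 scores adherence on 26 pre-, intra- and postoperative items, plus Audit. Among them are an item for avoiding routine bowel preparation, an item met by "Patient submitted to laparoscopic, robotic or video-assisted surgery", and an item met when "No drain is placed in the abdominal cavity".

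**The concern.** Patients who receive more of the ERAS items are likely to differ from those who receive fewer. Frailty, ASA class, nutritional status, indication and stage can each affect both adherence and outcome. Whether such a variable is needed in the model depends on its links with exposure and outcome, not on whether its own test reaches .05 in this sample. Several moderate confounders can each miss .05 and together still bias the adherence estimate. Taken literally, the rule would also leave adherence out of the adjusted model if adherence missed .05.

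The second problem runs the other way. A component that influences outcome is the kind of variable that passes the screen. Once it stands beside the score, the adherence coefficient no longer carries that component's share of the effect. Operative time and transfusion are also eligible, and both may partly follow from the care being scored.

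At stake is the adjusted adherence estimate for both primary endpoints. The two distortions can oppose each other, and a reader of the results could not tell which prevailed.

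**Working it through.** **1. The plan's own figures.** The covariate rule carries no figure. The sample sizes do, and they are unadjusted two-group contrasts at the 70% cut-off. Inputs (Sample size section): alpha 0.04, taken as two-sided; the stated beta of 0.8 read as power 0.80; ratio k = 2 below to above; 0.70 v 0.64 for PRO, treated as proportions; 6.5% v 13% for failure to RIOT.

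With p̄ = (p₁ + 2p₂)/3 and d = |p₁ − p₂|:

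n₀ = [2.054·√(1.5·p̄(1−p̄)) + 0.842·√(p₁(1−p₁) + p₂(1−p₂)/2)]² / d²

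Continuity-corrected: n = (n₀/4)·[1 + √(1 + 3/(n₀d))]².

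- PRO: p̄ = 0.66, n₀ = 776.1, n = 801 above; total 3 × 801 = 2,403 (stated 2,406).
- RIOT: p̄ = 0.1083, n₀ = 271.0, n = 294 above; total 3 × 294 = 882 (stated 885).

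Both reproduce to within 3 patients. Neither allows for covariates.

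**2. Overlap between risk factors and score.**

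| Recorded risk factor | Tab. 1 item | Where they differ |
|---|---|---|
| Bowel preparation | No bowel preparation | Item allows it if a covering stoma is anticipated |
| Type of approach | Minimally invasive surgery | Item counts conversions as adherent |
| Presence of drainage | No drain | Item allows a pelvic drain with a low anastomosis |

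Three of 26 items largely overlap; none is an exact copy. Nutritional status is not the same thing as the screening or prehabilitation items, and transfusion touches the anaemia item only in part.

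**3. What screening can omit (illustrative).** Assumed: true adherence odds ratio (OR) 1; eight independent binary confounders, each with prevalence 25%, OR 0.6 for adherence and 1.3 or 1.5 for the outcome; outcome risk about 11%; chi-squared screen at .05; adherence always kept; 300 replicates.

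| N | Confounder OR | Mean dropped, of 8 | Mean OR, all kept | Mean OR, screened | False positives, all kept / screened |
|---|---|---|---|---|---|
| 885 | 1.3 | 6.4 | 0.98 | 0.89 | 6.3% / 7.0% |
| 885 | 1.5 | 4.6 | 0.98 | 0.88 | 7.0% / 8.7% |
| 2,100 | 1.3 | 4.8 | 0.98 | 0.92 | 5.0% / 6.3% |
| 2,100 | 1.5 | 1.9 | 1.00 | 0.97 | 4.3% / 3.7% |

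The Monte Carlo standard error of the false-positive rates is about √(0.05 × 0.95/300) = 1.3 points.

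**4. What self-adjustment can remove (illustrative).** Assumed: 26 equally weighted items, each met by about 64% of patients; latent item correlation 0.1 or 0.3; outcome driven by the proportion of items met; no confounding; three items enter if p < .05; 300 replicates.

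| N | Correlation | OR, score alone | OR, components may enter | Power, alone / with components |
|---|---|---|---|---|
| 885 | 0.1 | 0.47 | 0.51 | 93% / 82% |
| 885 | 0.3 | 0.32 | 0.44 | 99.7% / 90% |
| 2,100 | 0.1 | 0.48 | 0.53 | 100% / 99.7% |
| 2,100 | 0.3 | 0.33 | 0.44 | 100% / 100% |

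**5. Can a fixed set be afforded for RIOT?** At N = 885: 295 × 0.065 + 590 × 0.13 = 19.2 + 76.7 ≈ 96 failures, or about 9 parameters at 10 events each. If all 2,100 expected malignant cases count, split 2:1: 1,400 × 0.13 + 700 × 0.065 = 182 + 45.5 ≈ 227 failures, or about 22 parameters.

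**The case against.** The strongest reply is that the rule is one generic sentence serving every endpoint. It does not cite the risk-factor list, and nowhere does the protocol say that the score and its items will share a model. For leakage and complications, approach and drainage are legitimate risk factors. A forced covariate list is commonly left to a statistical analysis plan, which may exist. The powered comparison is the unadjusted contrast, so a null adherence result would still be reported even if adherence failed the screen.

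Much of this stands as a limit on the point. Both harms depend on which variables pass, the overlap is partial, and the loss of adherence concerns only the adjusted model. The simulated bias from omitted confounders was modest, smaller at the larger N, and left false-positive rates near nominal. At N = 2,100 self-adjustment cost almost no power.

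It does not remove the point. The selection rule is stated in the protocol rather than left open, it covers all variables without exception, and an analysis plan that followed it would inherit the fault.

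A reader might go further and infer that the adherence effect is in fact under-controlled and adjusted for itself. The text supports only that it can be. A reader might also point to the chance that a pure-noise variable enters. Such a variable does not bias the adherence estimate, so that chance is no measure of the harm.

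**Conclusion.** The point holds in conditional form. For a non-randomised exposure, the stated rule can omit confounders, does not secure adherence a place in the adjusted model, and allows variables that largely overlap three of 26 scored items to stand beside the score.

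No single figure for the bias can be given. Under the assumptions above, screening moved a true OR of 1 to a mean of 0.88 to 0.89 at N = 885 and 0.92 to 0.97 at N = 2,100, in the direction of a spurious benefit because the confounders were set to lower adherence and raise risk. Letting components in moved the OR towards 1, from 0.47 to 0.51 or from 0.32 to 0.44 at N = 885. Confounder strengths, item prevalences, item weights and correlations are all assumed; the protocol gives none of them. Larger losses appear only if the three overlapping items are given extra weight, for which the protocol offers no basis.

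**What to change.** For the primary adherence models, replace the univariate screen with a pre-specified set of confounders not affected by adherence, kept whatever their p-values: age, sex, BMI, ASA class, frailty, nutritional status, comorbidity, steroid use, indication and pTNM stage, procedure and anastomotic level, and elective versus delayed urgency. Add the preoperative PRO score in the PRO models; the questionnaires are already given before surgery. Handle centre by a random effect or clustered standard errors; fixed effects for 60 centres would use 59 parameters. Always retain adherence.

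Leave bowel preparation, approach, drainage, operative time, transfusion and postoperative events out of these models. Approach may also carry confounding, for instance if open surgery is chosen for harder cases. So add it in a sensitivity analysis, with the score recomputed without that item.

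For RIOT, fit the set to the events expected: about 9 parameters at 885 patients and about 22 if all 2,100 malignant cases count. Near the lower figure, use a shorter set or a propensity score. The risk-factor models for leakage and complications may still include approach and drainage.

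The cost is analysis wording, slightly more analysis work and possibly slightly wider intervals. The variables are already recorded or known.

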Enhanced recovery pathways, patient-reported outcomes and return to intended oncological therapy after colorectal surgery: the Italian ColoRectal Anastomotic Leakage study group (iCral 3).

BACKGROUND

The ultimate goal of any surgery is to return the patient to at least their baseline functional status, if not an improved functional status compared with their preoperative state, as rapidly as possible and with the least amount of intercurrent disability. Enhanced Recovery After Surgery (ERAS) is a multimodal and multifactorial approach to the optimization of perioperative management (1, 2). In order to modify and improve the response to surgery-induced trauma, the program relies on a series of evidence-based items related to pre-, intra- and post-operative care (3). Several meta-analyses on ERAS showed a significant reduction of morbidity rates and length of stay after colorectal surgery (4-6). However, program implementation outside clinical trials is still extremely variable (7-9), as the necessary multidisciplinary involvement makes the program vulnerable to various areas of failure, that explain the great variation in adherence rates to program items (10-12).

During the early phase of program implementation, adherence rate to program items rarely goes beyond 50% (13), needing to reach at least 70% in order to significantly improve results (faster recovery and reduced morbidity). A recent cohort study conducted in 80 Spanish centers on about 2,000 patients recruited in 2 months (14) reported a mean adherence rate to ERAS items at 63.6%, reaching 72.7% in centers that declared to have an institutional program. A large multicenter study conducted on 2,352 patients undergoing colorectal resection in 13 centers in 6 different European countries also showed a mean overall adherence rate to ERAS items at 75% (15). In other studies, adherence to ERAS items was higher, reaching up to 90% (16, 17).

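### All named tests, both regressions and the sample size treat patients from 60 centres as independent, so p-values and intervals are too optimistic if adherence and outcome both correlate within centre

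*Protocol*

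**What the plan says.** Methods sets the structure: "Prospective enrollment from November 2020 to October 2021 in 60 Italian surgical centers", and "A total of 3,000 patients is expected based on a mean of 50 cases per center".

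Statistical Analysis names chi-squared or Fisher's exact tests for categorical data. For other variables it names "Student's two-sided t test (allowing for heterogeneity of variances) or with a non-parametric test" (Mann-Whitney or Kruskal-Wallis). Variables significant on univariate analysis then go into a multivariable step, where association "will be assessed using binary logistic or multiple linear regression". The threshold for every test is 0.05. Centre is not mentioned as a covariate, stratum, random effect or cluster, and it is not in the list of risk factors under Recorded data and follow-up.

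Sample size compares patients above and below 70% adherence, "with a 2:1 expected ratio below:above the cut-off". It gives 2,406 patients for patient-reported outcomes (PRO) and 885 for failure to RIOT. No ICC or design effect appears.

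Background describes uptake of ERAS programmes outside trials as highly uneven. It cites a Spanish cohort with mean adherence of 63.6%, "reaching 72.7% in centers that declared to have an institutional program".

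**The concern.** The named tests, and the two regressions in their ordinary form, take each patient as an independent observation. That fails when patients in the same hospital resemble each other in both exposure and outcome. The protocol gives a reason to expect this for the exposure: the two means it cites, 63.6% and 72.7%, lie on either side of the 70% cut-off that defines the comparison. For outcomes, it leaves imaging and additional examinations to each local surgeon's judgement, so detection of leaks and complications may differ between hospitals. That patient-reported outcomes or RIOT also cluster by hospital is plausible but is my inference.

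Two things are at stake. Standard errors would be too small, so the false-positive rate would exceed the stated 5%. And in a non-randomised comparison with no centre term, a hospital that both adheres better and has better results for other reasons contributes to the apparent effect of adherence.

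**Working it through.** **Inputs from the protocol.** 60 centres, 3,000 patients, mean 50 per centre (Methods). PRO 0.70 against 0.64, failure to RIOT 6.5% against 13%, ratio 2:1, alpha 0.04 and 70% malignant (Sample size). The sizing sentence reads "alpha 0.04, beta 0.8, the required sample size is" 2,406. The 0.8 is taken as power.

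**Step 1: reproduce the stated sizes.** No standard deviation is given for the PRO, so the two values are treated as proportions. With p1 the above-cut-off group, r = 2 and p̄ = (p1 + r·p2)/(r + 1):

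n1 = [z(1−α/2)·√((r+1)·p̄·(1−p̄)) + z(power)·√(r·p1(1−p1) + p2(1−p2))]² / [r·(p1−p2)²]

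with continuity correction n1′ = (n1/4)·[1 + √(1 + 2(r+1)/(n1·r·|p1−p2|))]².

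- PRO: p̄ = 0.66, z = 2.054 and 0.842, n1 = 776.1, n1′ = 800.9. This gives 801 + 1,602 = 2,403, against 2,406 stated.
- RIOT: n1 = 271.0, n1′ = 293.6. This gives 294 + 588 = 882, against 885 stated.

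Both agree within 3 patients, with no inflation for clustering. At alpha 0.05 the totals would be 2,256 and 828, which do not match.

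**Step 2: design effect.** For a patient-level exposure in centres of equal size m:

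DE = 1 + (m − 1) × ICC(exposure) × ICC(outcome)

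Effective N = N/DE. Type I error of a nominal 5% test = 2·[1 − Φ(1.96/√DE)]. Intervals should be wider by √DE. If either ICC is zero, DE is 1. Unequal centre sizes would generally raise it.

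**Step 3: PRO at the planned 3,000, m = 50, power at alpha 0.04.** All ICCs are assumptions.

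| ICC exposure | ICC outcome | DE | Type I error | Effective N | Power |
|---|---|---|---|---|---|
| any | 0 | 1.00 | 5.0% | 3,000 | 0.89 |
| 0.1 | 0.01 | 1.049 | 5.6% | 2,860 | 0.88 |
| 0.3 | 0.01 | 1.147 | 6.7% | 2,616 | 0.85 |
| 0.5 | 0.01 | 1.245 | 7.9% | 2,410 | 0.81 |
| 0.3 | 0.02 | 1.294 | 8.5% | 2,318 | 0.80 |
| 0.5 | 0.02 | 1.490 | 10.8% | 2,013 | 0.74 |
| 0.3 | 0.05 | 1.735 | 13.7% | 1,729 | 0.67 |
| 0.5 | 0.05 | 2.225 | 18.9% | 1,348 | 0.56 |

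Interval widening runs from √1.049 = 1.02 to √2.225 = 1.49.

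**Step 4: margin in the planned enrolment.** 3,000/2,406 = 1.247, so 3,000 absorbs a design effect up to about 1.25, which is an ICC product of 0.247/49 ≈ 0.005 (for example 0.5 × 0.01).

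**Step 5: RIOT.** 70% of 3,000 is 2,100, so m = 2,100/60 = 35. Over the same ICC ranges DE runs from 1 + 34 × 0.001 = 1.034 to 1 + 34 × 0.025 = 1.85. The requirement becomes 885 × 1.034 ≈ 916 to 885 × 1.85 ≈ 1,638, below 2,100 throughout. Power at 2,100 (alpha 0.04) stays between 0.996 and 0.92. Intervals should still be up to √1.85 = 1.36 times wider, and type I error is 5.4% to 15%.

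**Step 6: simulation check.** In 1,000 runs per setting of 60 centres of 50, an unclustered Welch test at 5% rejected a true null in 5% of runs with adherence unrelated to centre. It rejected in 8.4% at ICCs of 0.3 and 0.02, and in 15.3% at 0.5 and 0.05. Cluster-robust standard errors gave 4% to 6%. The 15.3% is below the formula's 18.9% because the simulated exposure ICC applies to the underlying score, and dichotomising at the cut-off lowers it.

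**The case against.** **The analysis plan is not shown and could supply this.** Logistic and linear regression are model families, and cluster-robust errors could be added without contradicting the wording. That is fair as far as the regressions go. It does not cover the named two-group tests, which have no such option in their ordinary form, or the sample size, which the protocol fixes under independence. Nor does the stated route bring centre in: only factors significant on univariate analysis enter the model, and centre is not among the listed factors.

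**A reader might infer that adherence is mainly a property of the centre.** The protocol does not support that. A difference of 9.1 points (72.7 − 63.6) between the programme centres and the overall mean in one foreign cohort says nothing about spread within centres. Table 1 scores adherence patient by patient, and several items, such as anaemia correction, catheter removal and mobilisation, can differ between patients in one hospital. The point needs only that both ICCs are positive.

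**A reader might also quote power at 2,406,** which over the same ICC ranges is 0.79 to 0.46. That is the calculated requirement; planned enrolment is 3,000, and the figures above use it.

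**The size of the effect is uncertain.** This stands. At the low end (0.1 and 0.01) type I error is 5.6%, which matters little.

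**Conclusion.** The point holds conditionally. As written, the analysis and the sizing ignore centre, and the protocol itself gives grounds to expect adherence to vary by centre. The direction is clear if both ICCs are positive: intervals too narrow, p-values too small, and hospital differences open to being read as adherence effects. The size cannot be fixed from the protocol and ranges from slight to substantial over the ICCs assumed here. The loss of power concerns the PRO endpoint and drops below the planned 0.80 once the design effect passes roughly 1.25 to 1.3. A conclusion that RIOT is underpowered would not be supported; for that endpoint the issue is the validity of intervals and p-values.

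The calculations assume equal centre sizes, PRO values treated as proportions, and the sizing alpha of 0.04 for power. The analysis section states another level ("For all statistical tests the significant level is fixed at" p < .05), which is why type I error is shown for a 5% test. That mismatch is a separate matter.

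**What to change.** In Statistical Analysis:

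- Make the primary adherence models for the PROs and RIOT linear or logistic models with a random centre intercept, or ordinary models with centre-clustered robust standard errors.
- Name centre as a recorded analysis variable. Upload by local investigators suggests that it is known, but it is not listed.
- Label the unclustered univariate tests as descriptive.

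In Sample size, state that 2,406 and 885 assume independent patients, and give power at 3,000 (2,100 for RIOT) over a stated ICC range, as in the table above.

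Clustered errors repair precision only; they do not separate hospital differences from adherence. Adding each centre's mean adherence as a further term would split the within-centre from the between-centre association. This is a useful optional sensitivity analysis, not a correction the protocol needs.

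The change is to wording and analysis only. It needs no extra patients or visits, and the Stata software already named can fit these models. The price is wider confidence intervals and a somewhat less favourable stated power. If clustering proves negligible, almost nothing is lost.
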